Cover page for clinical trials.gov

Official Study Title: Socio-Structural Intervention to Improve Pre-Exposure Prophylaxis Services for Cisgender Women (PrEP CGW)

NCT number: pending

Date of Document: May 3, 2021

STATISTICAL DESIGN & POWER

Aim 1: Intervention Development. We will recruit n=10 key informants for in-depth interviews and up to n=60 CGW and medical providers to contribute to the focus groups (2-3 groups per population with groups of 8-10 participants) and theater testing.

Aim 2: Feasibility Trial. Given the pilot nature of this study, it is not appropriate to conduct a power analysis; We are not testing effectiveness during this stage of the trial.¹

Measures & Analysis. Data collection will be ongoing in through the EMR; reach and initial effects data will be extracted for all CGW at three time points (baseline, intervention, and discontinuation). More detailed data in regard to the intervention strategies (provider training and peer navigation) will be collected on Adoption and Implementation (feasibility and acceptability) at the end of the intervention time period as described in **Table 1** below.

Table 1. Aim 2 Outcomes, Data Sources, and Time Points for Evaluation

Outcome	Data Source/ Measure	Time of Evaluation*
Reach (also shows feasibility of intervention)		
% of eligible CGW counseled on PrEP by providers	EMR	Year 3, Quarter 2 (End of Intervention)
% of CGW who complete HIV prevention discussion with peer navigator	Comparison of peers' patient log with EMR patient visit log	Year 3, Quarter 2
Measure of Initial Effects (note: no statistical testing for effectiveness in pilot phase; measures are for feasibility of data collection and standard deviation calculation)		
% change in perceived medical bias	7-item Discrimination in Medical Settings Scale	Year 2, Quarter 3 & Year 3 Quarters 1&2
% eligible CGW initiate PrEP	EMR	Year 3, Quarter 2
Of CGW who initiate PrEP, % adherence at 1 month	EMR, DBS**, & Pharmacy Data	Year 3, Quarter 2
Of CGW who initiate PrEP, >75% will persist \geq 1 month	EMR & Pharmacy Data	Year 3, Quarter 2
Adoption		
% of providers who participate in synchronous or asynchronous training	Attendance log	Year 3, Quarter 2
% change in knowledge/awareness of medical bias and positive PrEP counseling techniques	Provider training module pre- & post-knowledge questionnaires	Year 2 Quarter 4- Year 3 Quarter 1
Implementation		

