Perceived feasibility of implementing the intervention	Provider & Peer Likert scale survey & Provider & Peer in-depth interviews (n=10)	Year 3, Quarter 2
Acceptability: % CGW who receive provider counseling or peer session and report high satisfaction	CGW; Likert scale survey to rate affective attitude, or feelings towards the intervention, burden, or perceived amount of effort to participate, and congruence with individual values ²	Year 3, Quarters 1-2 (Post-clinical visit or peer session)
Satisfaction with training (synchronous vs. asynchronous) and outreach intervention among providers and peers	Provider & Peer Likert scale survey; Provider & Peer in-depth interviews (n=10)	Year 2 Quarter 4 - Year 3 Quarter 2 (Beginning, mid, & end of intervention) Year 3, Quarters 1-2
Organizational perspective on the intervention	Provider & Peer in-depth interviews (n=10)	Year 3, Quarters 1-2
Patient perspective on the intervention	Patient in-depth interviews (n=20)	Year 3, Quarters 1-2

*See **Study Timeline** in PHS

For percentage outcomes we will use the following “traffic light” benchmark system for feasibility and acceptability in Aim 2: 0-50%: failure of the current intervention design; 51-75%: major revisions required; 76%: no or minor revisions needed for a confirmatory trial.

Questionnaires. RAs will invite all CGW seen in FPPC to participate in a 5-minute tablet-based survey to assess acceptability of the provider and peer components of the intervention and intention to initiate PrEP; CGW seen virtually will be contacted by phone and/or email and invited to participate in an online survey. We anticipate that approximately 300 CGW will complete the survey. Upon survey completion, participants will be invited to provide their contact information to participate in virtual or in-person IDI. Additionally, to assess intermediate effects of the provider trainings, we plan to use the 7-item Discrimination in Medical Settings Scale³, which has been validated in Black populations, to capture changes in patient-reported experiences before and after implementation of trainings to capture participant perceptions of bias.

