Adoption by providers will be measured using attendance logs, with the goal of >75% of providers completing trainings. Additionally, we will evaluate the educational impact of the provider trainings with pre- & post-knowledge questionnaires for all training participants. **Implementation** outcomes focus on feasibility and acceptability, which will be evaluated both quantitatively and qualitatively. For quantitative measures we will use a validated, 8-item Likert scale to be completed by providers and peer navigators.⁴ We will also use the Theoretical Framework for Acceptability, with seven domains on a Likert scale to assess ethicality, affective attitude, experienced burden, opportunity costs, perceived effectiveness, self-efficacy, and intervention coherence.²

Feasibility and Acceptability will also be assessed in qualitative, in-depth interviews with patients and providers. Transcripts will be uploaded into the qualitative data analysis software, *Atlas.ti*,^{5,6} for the purposes of coding and analysis. We will first develop an *a priori* code book⁶ that reflects key analytic concepts related to topical areas described above contained in the semi-structured interview guide. During the process of reading and coding of transcripts using this initial coding scheme, additional codes may be added to document emerging domains of interest. Qualitative analysis will proceed by first exploring broad patterns of perspectives and experiences. For FGDs, we will look for patterns of consensus and divergence within groups, and comparative perspectives between groups e.g., potential PrEP users and providers in terms of receptiveness for intervention plans for both the provider trainings and peer navigation components. For IDIs, we will assess similarities and differences between types of participants for patients and providers, respectively, (e.g., variation by demographics, level and type of engagement) and then across the groups to gain insight into how the intervention was received and variation in acceptability.

These qualitative and quantitative data will then be triangulated to refine the interventions for the future full-scale trial.

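### Do the whole-percent traffic-light bands leave results ungraded, clash with the SAP's >75% goals, or wrongly grade change scores?

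*SAP*

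**What the plan says.** The rule stands under Table 1 in the Aim 2 section of the SAP. It begins "For percentage outcomes we will use the following" and is described as a "benchmark system for feasibility and acceptability in Aim 2". The bands are "0-50%: failure of the current intervention design; 51-75%: major revisions required; 76%: no or minor revisions needed for a confirmatory trial". The text at hand shows no sign in front of 76%. One may have been lost when the PDF was read, so the last band is taken here as 76% and above.

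Two numeric goals appear elsewhere in the SAP:

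- Provider training (Adoption paragraph): "with the goal of >75% of providers completing trainings".
- One-month persistence (Table 1, Initial Effects block): "Of CGW who initiate PrEP, >75% will persist" for at least one month.

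Three places bear on which rows the bands grade:

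- The Reach block is headed "Reach (also shows feasibility of intervention".
- One row in the Implementation block reads "Acceptability: % CGW who receive provider counseling or peer session and report high satisfaction".
- The text says that Implementation "outcomes focus on feasibility and acceptability, which will be evaluated both quantitatively and qualitatively".

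Table 1 also has two rows expressed as a percentage change: perceived medical bias (Initial Effects) and knowledge or awareness (Adoption).

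**The concern.** Three things look wrong at first.

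1. **Gaps.** The bands end and restart on consecutive whole numbers. An unrounded proportion such as 50.4% or 75.6% belongs to none of them, and the SAP states no rounding convention.
2. **A different top cut.** The two stated goals are >75%, while the top band starts at 76%. A result just above 75% could meet a goal and still be graded as needing major revision.
3. **Scope.** The rule speaks of percentage outcomes and does not list rows. Bands running from 0% upward suit attainment proportions. A fall in perceived bias reported as a signed change would be negative and have no band, although it is the desired direction.

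These bands are the SAP's numeric benchmark for readiness for a confirmatory trial. If they left results ungraded, or graded them against the SAP's own goals, the sponsor could choose the grade after seeing the data.

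**Working it through.** **Inputs.** Bands 0-50, 51-75 and 76% (SAP, below Table 1). Goals of >75% (Adoption paragraph; Table 1 persistence row). About 300 expected survey completers (Questionnaires paragraph). 460 women in the intervention period (sample-size paragraph). The last two are illustrative denominators only: the Acceptability row counts just those who had counselling or a peer session, and the counselling row just those eligible. There is no sample size, power or alpha to reproduce, because the bands are a descriptive rule.

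**Step 1: ungraded results without rounding.** List every k with 0.50 < k/N < 0.51 or 0.75 < k/N < 0.76.

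| N | Between 50% and 51% | Between 75% and 76% |
|---|---|---|
| 300 | 151 (50.33%), 152 (50.67%) | 226 (75.33%), 227 (75.67%) |
| 460 | 231-234 (50.22-50.87%) | 346-349 (75.22-75.87%) |

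The smallest N at which a gap can be hit is 51 for the lower gap (26/51 = 50.98%) and 29 for the upper gap (22/29 = 75.86%).

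**Step 2: how likely the upper gap is.** The chance is the sum of the binomial probabilities P(X = k | N, p) over the k in the last column of the table.

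| True rate p | N = 300 | N = 460 |
|---|---|---|
| 0.70 | 0.011 | 0.005 |
| 0.75 | 0.105 | 0.166 |
| 0.80 | 0.018 | 0.012 |

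The chance is noticeable only when the true rate lies at the cut. Five points away it is below 2%.

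**Step 3: round to whole percents.** Every proportion then has a band.

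- N = 300: 151 rounds to 50% (first band), 152 to 51% (second), 226 to 75% (second) and 227 to 76% (third).
- N = 460: 231-232 round to 50% (first band), 233-234 to 51% (second), 346-347 to 75% (second) and 348-349 to 76% (third).

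Among whole percents, the values above 75 are exactly 76, 77 and so on, so the top band and a >75% goal coincide.

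**Step 4: what is left of the clash with the goals.** If the goal is judged on the unrounded value and the band on the rounded one, they disagree for 75% < k/N < 75.5%. The smallest N that allows this is 53 (40/53 = 75.47%). Among N = 1 to 100 it is possible at only 12 values: 53, 57, 61 and so on in steps of four up to 97. The clash also needs a graded row that carries a >75% goal. Those rows are providers trained and persistence among women who start PrEP, and the SAP gives neither denominator. The 300 and 460 belong to neither row, so they cannot be used to size this clash.

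**Step 5: which rows are graded.** Set the scope wording against the blocks of Table 1.

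| Row | Block | Tied by the SAP to intervention feasibility or acceptability? |
|---|---|---|
| Counselled on PrEP; peer discussion completed | Reach | Yes, by the block heading |
| High satisfaction | Implementation | Yes, named as acceptability |
| Persistence (>75%) | Initial Effects | No; the heading mentions only feasibility of collecting data |
| Perceived bias, change | Initial Effects | No; same heading |
| Providers trained (>75%) | Adoption | Not stated |
| Knowledge, change | Adoption | Not stated |

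On this reading the graded rows are three attainment proportions. Neither goal row and neither change row is among them.

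**The case for a change.** The best case for a change is that rounding does not settle everything. It moves the effective top cut to 75.5%, so 40 of 53 providers trained would meet the stated goal and yet, if that row is graded, be told that major revision is needed. Nor is the narrow scope beyond doubt: the rule opens broadly, lists no rows, and the Initial Effects heading itself uses the word feasibility. Contiguous limits and a list of rows would cost a sentence or two and no data, and are best written before results are seen.

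The facts in this case stand. The SAP states no rounding rule and no list of rows. The inference is weaker:

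- The mismatch after rounding needs a goal row to be graded, a denominator of at least 53 that allows such a value, and a result inside a half-point window.
- The Initial Effects heading concerns whether data can be collected and standard deviations estimated. That is not attainment of 76% on a bias scale.
- Grading a change score against bands that start at zero makes so little sense that an analyst would not do it, and the SAP nowhere says to.

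The cheapness of an edit does not show that the plan as written leads to a wrong conclusion.

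**Conclusion.** The concern does not call for a change. What remains is an unstated rounding convention and an unlisted scope, and an analyst would fill both sensibly: round to whole percents, and grade the attainment proportions that the SAP ties to feasibility and acceptability. Done that way, every graded result has a band and no stated goal is contradicted.

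Without rounding, each gap is less than one point wide. With rounding, the only possible disagreement with a >75% goal is the window from just above 75% to just below 75.5%, and only if the training or persistence row is graded.

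Little depends on that edge. The SAP tests no effectiveness in this pilot, plans a descriptive summary of the Table 1 outcomes, and combines the quantitative results with interviews to refine the intervention. It ties no band to an automatic decision, and a team would hardly plan differently at 75.3% than at 76%.

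This rests on three assumptions: the last band means 76% and above, the bands are in whole percents, and the scope wording is meant to limit the rows graded. The first two are the ordinary reading of such bands. The third is the more likely reading but not certain; if it failed for the goal rows, only the half-point window would be affected.

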Quantitative data will be entered into REDCap for structured data storage and analyzed using Python/R language. We will conduct a descriptive summary of the outcomes described in the above Table 1. Where appropriate, we will test item scale reliability using the intraclass correlation coefficient (ICC). In surveys we will also collect data on demographics (e.g., race, age, education, income, partner status), behavioral risk for HIV (e.g., number of sexual partners, HIV status of partner, consistency of condom use), medical history (e.g., comorbidities, duration of risky behaviors), and lifestyle habits (e.g., smoking, alcohol consumption, substance abuse). We will also describe the demographic and clinical characteristics of CGW included in the sample, including means (standard deviations) or medians (interquartile ranges), and frequencies (percentages). Following descriptive statistics, we will compare the proportions of CGW who initiate PrEP and persist ≥ 1 month by key characteristics (e.g., age, partner status). We will use logistic regression to explore characteristics of those initiating PrEP and continuing past one month.

In order to better estimate treatment standard deviations, we will explore RDD analyses in preparation for our future effectiveness trial. RDD is a quasi-experimental, pretest-posttest design, it is commonly used for causal research studies, which involve distinct cutoff values that assign subjects into different conditions and compare different conditions' outcomes. In the full-scale effectiveness trial, we will isolate the treatment effect by designing a baseline period (months 6-9 in year 2) and intervention period (month 12 year 1 to month 3, year 3), and will determine the cutoff points before the data collection. The design allows an unbiased estimate of the treatment effect by minimizing confounding bias and assessing the magnitude of the discontinuity on outcomes at the cutoff point. We will also consider potential confounders of demographics factors including age, income, partner status in the analysis to achieve comparability and exchangeability.

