Capperlieri et.al. conducted a power analysis using $\alpha = .025$ (one-tailed) and provided recommendations for the sample sizes for detecting different standardized effect sizes.⁷ Their results show: 1) a sample of 1078 would have a power of .80 for detecting a small effect size, 2) a sample of 150 would have a power of .80 for detecting a medium effect size, 3) a sample of 68 would have a power of .80 for detecting a large effect size, and 4) a sample size of 109 would have power of .95 for detecting a large effect size. While we are not conducting effectiveness testing at this stage, our numbers should allow for calculation of standard deviations to prepare for our fully powered trial. Based on their study, we will recruit an adequately sample size of CGW participants for the preliminary RDD analysis (i.e., 460 CGW participants during the intervention period, an additional 345 CGW participants in the baseline, and 460 in the discontinuation period).

[name] will conduct analyses in PythonR⁸. All data reporting will follow the CONsolidated Standards of Reporting Trials (CONSORT) guidelines.⁹

5. ATLAS.ti: The Qualitative Data Analysis & Research Software. Accessed January 7, 2021. <https://atlasti.com/>

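### Is the exploratory regression-discontinuity analysis misdirected because the SAP justifies it by standard deviations and does not list the standard error of the discontinuity?

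*SAP*

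**What the plan says.** The RDD paragraph of the SAP opens with the purpose: "In order to better estimate treatment standard deviations, we will explore RDD analyses in preparation for our future effectiveness trial". It then says that the design works by "assessing the magnitude of the discontinuity on outcomes at the cutoff point", and describes the later full-scale trial as having a "baseline period (months 6-9 in year 2) and intervention period (month 12 year 1 to month 3, year 3").

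Three other places bear on the point.

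- The paragraph on quantitative data, just before it, says: "We will conduct a descriptive summary of the outcomes described in the above Table 1".
- Table 1, in the heading for initial effects, rules out effectiveness testing and says that the "measures are for feasibility of data collection and standard deviation calculation".
- The sample-size paragraph says that "our numbers should allow for calculation of standard deviations to prepare for our fully powered trial", and gives the pilot numbers as "460 CGW participants during the intervention period, an additional 345 CGW participants in the baseline, and 460 in the discontinuation period".

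The Measures & Analysis text adds that "reach and initial effects data will be extracted for all CGW at three time points". No place lists an SE or confidence interval for the discontinuity.

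**The concern.** An RDD is a way to estimate a jump at a cutoff, not a way to improve an SD. Counseling, initiation and persistence are yes/no outcomes, so the SD is fixed once the proportion is known. For the discrimination scale and adherence, the planned descriptive summary already supplies it.

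The later trial is described as a comparison across a cutoff in calendar time. Period and time are then strongly correlated, and the jump is estimated much less precisely than a plain difference between periods. A planner who took only an SD from the pilot and used a plain two-group formula would make that trial too small. On this reading the pilot analysis is run for a quantity it does not improve, while the quantity needed goes unnamed.

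**Working it through.** **The plan's own figures.** The SAP states no SD or SE. Its only related figures are the cited sizes 1078, 150, 68 and 109, which are not in dispute. Its effect sizes are undefined. If they are f-squared values of 0.02, 0.15 and 0.35 (assumed), with a design factor of 1/(1 − 2/π) = 2.75, the sizes come out at 1082, 146, 64 and 105. So the cited figures appear to carry an RDD penalty already.

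**1. Does the RDD improve the SD?**

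- Yes/no outcome: SD = √(p(1−p)). At an assumed 20% this is √(0.2 × 0.8) = 0.40.
- Relative SE of an SD (normal outcome) = 1/√(2(n−1)): 3.8% for n = 345 and 3.3% for n = 460, without any RDD.
- Simulation (2,000 data sets, 345 and 460 women, mild trend and a jump, no covariates): pooled within-period SD against RDD residual SD was 0.3964 against 0.3962 (yes/no) and 1.0010 against 0.9996 (continuous). Sampling error was practically equal for the two methods.
- Trend needed for a visible gain: a slope of b residual SDs per month adds b²L²/12 to the variance in a period of L months. With 3 and 4 months the weighted mean of L²/12 is (345 × 0.75 + 460 × 1.333)/805 = 1.083. For the residual SD to be 5% lower, 1.083b² = 1/0.95² − 1 = 0.108, so b = 0.32 SD per month, which is a steep trend.
- Covariates: a 5% lower SD needs R² = 1 − 0.95² = 0.0975. The RDD paragraph plans to consider age, income and partner status, and an adjusted SD is something the descriptive summary does not give.

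**2. What does the RDD cost in precision?** Assumptions: linear trend, steady arrivals, equal variance, independent women, and the intervention start printed as year 1 read as year 2 (otherwise it would precede the baseline).

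Unadjusted SE at 20% = 0.4 × √(1/345 + 1/460) = 0.4 × √0.005072 = 0.0285.

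Common slope: variance ratio = 1 + d²/(S × 0.005072), where d is the distance between period midpoints in months and S = Σ nL²/12.

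| Reading | Calculation | Ratio | SE |
|---|---|---|---|
| Adjacent, 3 and 4 months, common slope | d = 3.5, S = 872.1 | 3.77 | 0.0553 |
| Adjacent, separate slopes | edge of a uniform span | 4.00 | 0.0570 |
| Printed months counted inclusively (two-month gap), common slope | d = 6, S = 1073.3 | 7.61 | 0.0786 |
| Same, separate slopes, cutoff at month 12 | (13/345 + 4/460)/0.005072 | 9.14 | 0.0861 |
| Three-month spans, three-month gap | common to separate slopes | 12.8–17.7 | – |
| Discontinuation period added, immediate return to baseline | common slope | about 1.0 | – |
| Discontinuation period added, own effect | common slope | 2.6–5.2 | – |

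With unequal proportions the ratio shifts. At 10% against 20% the fourth row becomes (13 × 0.09/345 + 4 × 0.16/460)/(0.09/345 + 0.16/460) = 7.86.

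**3. What follows.** The ratios come almost wholly from period lengths, the gap and the model. None needed pilot data beyond the assumed counts and, where variances differ, the proportions. They can be computed at a desk once the later trial's calendar is set. The outcome SD or proportion cannot.

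**The case for a change.** The strongest case for a change is that the document misstates why an analysis is run and leaves its most useful result unnamed. A plain two-group calculation from the pilot SD would undersize a calendar-cutoff trial about fourfold (3.77) to ninefold (9.14) for baseline against intervention. The cited sizes, if they carry a factor near 2.75, cover only part of that, since 3.77/2.75 = 1.4 and 9.14/2.75 = 3.3. Correcting the text would cost a few sentences and no data.

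Part of this stands. The purpose sentence is loose, it does not define treatment standard deviations, and outcome SDs alone would not size a trial analysed by RDD.

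The rest is weaker. An RDD regression does return a residual SD, adjusted for trend and possibly for covariates, and that is a legitimate planning input, so the stated purpose is not empty. The paragraph names the size of the discontinuity, and its SE comes with the estimate in any regression output. The undersizing would occur only if a later planner ignored the design, and that calculation is not in this document. The penalty also has no single value: it runs from about 1.0 to 17.7 across readings, and the printed months belong to the full-scale trial while the counts are the pilot's. Rewriting the paragraph around chosen outcomes would settle a choice that the plan leaves open for an exploratory analysis.

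**Conclusion.** No change is needed. Followed as written, the plan gives sound proportions and SDs by period, an exploratory discontinuity estimate and, as a matter of course, its SE. No effectiveness test depends on the wording, and the SAP does not size the later trial.

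The SE of the discontinuity is about 1.9 to 3.0 times the unadjusted one for baseline against intervention (√3.77 to √9.14). That rests on a linear trend, steady arrivals, equal variance, inclusive counting of months and the corrected start year. It is higher if the months are read as three-month spans, and there is no penalty if the discontinuation period is used and outcomes return at once to baseline. This matters to whoever designs the full-scale trial, who can derive it from that trial's calendar. The SD comparison rests on simulations with mild trends and no covariates; a steep trend or strong covariates would make the RDD residual SD more informative, which favors the plan's wording.

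### As printed, the RDD intervention period starts six months before the baseline and contains all of it; the start year is probably a slip and should be corrected

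*SAP*

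**What the plan says.** The RDD paragraph under Measures & Analysis is the only place in the SAP that dates the analysis periods by month: "designing a baseline period (months 6-9 in year 2) and intervention period (month 12 year 1 to month 3, year 3". The sentence opens "In the full-scale effectiveness trial, we will isolate the treatment effect" and goes on to say that the investigators "will determine the cutoff points before the data collection".

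Four other places bear on these dates:

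- **Measures & Analysis, opening:** "reach and initial effects data will be extracted for all CGW at three time points (baseline, intervention, and discontinuation".
- **Sample size paragraph:** 460 women are planned for the intervention period, a further 345 for the baseline and 460 for the discontinuation period, all for a preliminary RDD analysis.
- **Table 1:** provider and peer satisfaction is timed "Year 2 Quarter 4 - Year 3 Quarter 2 (Beginning, mid, & end of intervention"; the provider pre/post knowledge questionnaires "Year 2 Quarter 4- Year 3 Quarter 1"; perceived medical bias "Year 2, Quarter 3 & Year 3 Quarters 1&2".
- **Questionnaires:** the bias scale is used "to capture changes in patient-reported experiences before and after implementation of trainings".

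**The concern.** A pretest-posttest comparison by period needs a point in time with baseline on one side and intervention on the other. The printed dates provide none, because the baseline sits in the middle of the intervention. A cutoff in calendar time cannot be fixed in advance from such periods, and there is no break at which to measure a discontinuity.

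At stake is which women count as baseline and which as intervention. If the dates govern the pilot's preliminary RDD, an analyst who applied them to the medical record extract would put every woman seen in the baseline months into both groups. If they govern only the full-scale trial, the same fault passes into the design that the pilot is meant to prepare.

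**Working it through.** **Conversion.** Study month = 12 × (year − 1) + month.

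| Period | As printed | Study months |
|---|---|---|
| Baseline | year 2, months 6 to 9 | 12 + 6 = 18 to 12 + 9 = 21 |
| Intervention | year 1, month 12 to year 3, month 3 | 0 + 12 = 12 to 24 + 3 = 27 |

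**Overlap as printed.**
- Intervention length, inclusive: 27 − 12 + 1 = 16 months.
- Start relative to baseline: 18 − 12 = 6 months earlier.
- Baseline months inside 12-27: 18, 19, 20 and 21, so 4 of 4. Containment is complete whether the baseline is counted as four inclusive months or three elapsed months.

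**Comparison with Table 1.** This applies if the dates are the pilot's and assumes that Quarter 1 of each study year is months 1-3. Then Year 2 Quarter 3 = months 19-21, Year 2 Quarter 4 = 22-24, Year 3 Quarter 1 = 25-27 and Year 3 Quarter 2 = 28-30.
- Table 1 puts the beginning of the intervention in months 22-24. The printed start is 22 − 12 = 10 to 24 − 12 = 12 months earlier.
- The provider training questionnaires run over months 22-27. The printed start precedes that window by the same 10 months or more.
- The first bias measurement, meant to precede the trainings, is in months 19-21. That is 19 − 12 = 7 to 21 − 12 = 9 months after the printed start.

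**Start read as year 2.** Month 12 of year 2 = 12 + 12 = 24, so the intervention is months 24-27.
- Overlap with months 18-21: 0.
- The start falls in Year 2 Quarter 4, as in Table 1, and the window lies inside months 22-27.
- The first bias measurement (19-21) now precedes it.

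**Planned numbers, as a rough check.** This assumes constant monthly accrual, which the SAP does not state.
- Baseline counted as four months: 345 / 4 = 86.25 women per month. Sixteen months would give 86.25 × 16 = 1,380.
- Baseline counted as three months: 345 / 3 = 115 per month. Sixteen months would give 115 × 16 = 1,840.
- The plan has 460. Four months at 115 gives exactly 460, although that match counts the baseline as three months and the intervention as four. At 86.25, four months gives 345.

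On either count, 460 is much closer to a four-month intervention than to a sixteen-month one. The conclusion does not depend on this check.

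**The case against.** The strongest objection concerns weight, since the dates themselves are not in dispute. The sentence names the full-scale effectiveness trial, so read literally it does not govern the pilot's data. No hypothesis test and no traffic-light benchmark uses these dates. The fault is probably a single digit, and a reader can recover the intended order from the rest of the SAP. Table 1 also refers to a Study Timeline that is not shown, and staff might work from that instead.

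Most of this stands, and it limits the harm. Double classification of women follows only if the dates are applied to the pilot. There are grounds to think they might be: they share the Year 2-3 calendar of Table 1, and the sample size paragraph plans a preliminary RDD on the same named periods. The overlap is in any case internal to one sentence, so it is wrong for whichever trial is meant.

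Two supporting points are inferences. The list of baseline, intervention and discontinuation is a natural chronological order but not a stated rule. The SAP does not name the variable on which the cutoff is set; calendar time is the likely reading because the conditions compared are periods. The stronger evidence of separate periods is that the 345 baseline women are counted in addition to the 460.

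**Conclusion.** The point holds. The printed intervention period runs over study months 12-27, starts six months before the baseline and contains all of it; no other text in the SAP resolves this. The arithmetic needs only the one sentence. The comparison with Table 1 rests on the quarter convention and on the dates being the pilot's.

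Reading year 1 as a slip for year 2 is an inference. It is well supported, because it cuts the overlap from four months to none and puts the start in Table 1's quarter. It does not settle every detail. Baseline month 6 falls in Year 2 Quarter 2, whereas Table 1 takes the first bias measure in Quarter 3. The month-27 end comes one to three months before the Year 3 Quarter 2 entry that Table 1 labels as end of intervention. That is not a demonstrated conflict, because the column gives the time of evaluation.

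The fault should be corrected, but its consequence is modest: the RDD is exploratory and serves to plan a later trial.

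**What to change.** In the RDD paragraph:

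1. Correct the year in which the intervention period starts.
2. State baseline and intervention periods that do not overlap and that agree with Table 1 and the Study Timeline. The sponsor chooses the dates.
3. Say whether these periods apply to the pilot's preliminary RDD or only to the full-scale trial.
4. As a minor clarification, say whether the Year 3 Quarter 2 entry in Table 1 marks the end of delivery or the evaluation that follows it.

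This changes SAP wording only, with no extra participants or procedures.
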